6.13.7. Open Sessions

The study team will review masked information relating to study progress and data collection with

the DSMC members between the Closed Sessions.

6.13.8. Open and Closed Reports

As needed, Open and Closed Reports will be provided for each DSMC meeting. Open Reports will include data on recruitment and baseline characteristics, eligibility, and completeness of follow-up and compliance in aggregate. The DCC will prepare these Open Reports.

Closed Reports, available only to those attending the Closed Sessions of the meeting, will include analyses of primary and secondary efficacy endpoints, including subgroup and adjusted analyses, adverse events, and Open Report analyses that are displayed by intervention group. Closed Reports will be prepared by the unmasked study biostatistician and data analyst. No unmasked interim data will be reviewed during closed reports until primary analysis data has become available.

The Open and Closed Reports should summarize data collection that has been completed by at most two months before the date of the DSMC meeting. The Reports should be provided to DSMC members at least three days prior to the date of the meeting.

6.13.9. Minutes of the DSMC Meetings

The research team will prepare minutes for the open portion of the meeting, including the DSMC's recommendations.

6.12.10. Recommendations to the Executive Committee

At each meeting, the DSMC will make a recommendation to the Executive Committee to continue or terminate. This recommendation will be based primarily on safety and efficacy considerations and will be guided by statistical monitoring guidelines defined in this Charter.

Recommendations to amend the protocol or conduct of the study made by the DSMC will be considered and accepted or rejected by the Executive Committee. The Executive Committee will be responsible for deciding whether to continue or to stop the trial based on the DSMC recommendations.

The DSMC will be notified of all changes to the study protocol or to study conduct. The DSMC concurrence will be sought on all substantive recommendations or changes to the protocol or study conduct prior to implementation.

The Executive Committee may communicate information in the Open Report to the sponsor and may inform them of the DSMC recommended alterations to study conduct or early trial termination in instances in which the Executive Committee has reached a final decision agreeing with the recommendation. The Executive Committee will maintain confidentiality of all information it receives other than that contained in the Open Reports until after the trial is completed or until a decision for early termination has been made.

6.14. Policy Matters

Any changes to the protocol made during the course of the study will be incorporated into the revised study protocol and procedures and recorded in a change log. Any new forms will be incorporated as an addendum. All protocol changes will be submitted and approved by the IRB

of both collaborating centers as required. Major changes will also be submitted to DSMC.

## 2. Overview

The AVENIR study includes multiple different trials, each with different objectives (Figure 1). This Statistical Analysis Plan (SAP) includes details for the Mortality and Resistance Trial. Separate SAPs cover the Delivery and Programmatic trials.

### Phase I Summary of the design

Figure 1. Phase I summary of design.

\*A random sample of 150 communities was selected for AMR monitoring, 60 of which contribute to the primary

### Trial masking

The Mortality/Resistance trial is a double-masked, placebo controlled trial. All participants are masked to their treatment. Study investigators and field staff are masked to treatment with the

exception of the unmasked portion of the trial analysis team at UCSF. The unmasked portion of the analysis team will conduct the response adaptive allocation and pre-specified interim analyses. Unmasked members include one of the four PIs for the trial ([name]), one of the two biostatisticians for the trial ([name]), and one analyst ([name]). These members were designated in January 2022 before any adaptation or interim analyses would commence. The rationale for including this composition of the unmasked analysis team was to ensure sufficient statistical and subject matter expertise to guide the critical interim discussions and decisions for the response-adaptive trial, in coordination with the trial's Data and Safety Monitoring Committee.

The Delivery Trials and Programmatic Trial are unmasked and do not include a placebo.

## 3. Mortality Trial

### 3.1. Introduction

#### 3.1.1. Background and rationale

This document (Statistical Analysis Plan, SAP) describes the planned analysis and reporting for the clinical trial, L'azithromycine pour la vie des enfants au Niger: implémentation et recherche (AVENIR). It includes specifications for the statistical analyses and tables to be prepared for the final Clinical Study Report. This study is a Phase IV clinical trial to compare methods to reduce childhood mortality using mass administration of azithromycin (Pfizer, CAS 83905-01-5) compared to placebo.

#### 3.1.2. Objectives

AVENIR is designed to assess the efficacy of mass distribution of azithromycin to prevent mortality among children.

The overall objectives of this study are to:

1. Determine the optimal age group to treat with biannual oral azithromycin distribution to reduce child mortality
2. To compare selection for antimicrobial resistance across different age-based strategies for biannual azithromycin distribution
3. Demonstrate large-scale implementation of this program.

## 3.2. Study Methods

### 3.2.1. Trial design

AVENIR is designed as a large simple double-masked cluster-randomized trial with response-adaptive allocation (a platform, perpetual trial). The rationale for adaptive randomization is to allow all communities to have the opportunity to be treated, and to allow the program to evolve into the optimal treatment. If new treatment arms are added to AVENIR in the future, or if any of the current treatment arms are discontinued, the Protocol and SAP will reflect those updates.

Eligible communities in Niger will be randomly selected to participate in a mortality/resistance trial, a delivery trial or a delayed intervention.

In the mortality/resistance trial, communities will be randomized to one of three azithromycin distribution strategies: 1) **azithro 1-11**: biannual oral azithromycin to children 1-11 months old with biannual oral placebo to children 12-59 months old, 2) **azithro 1-59**: biannual oral azithromycin to children 1-59 months old, or 3) **placebo**: biannual oral placebo to children 1-59 months old. Mortality will be monitored through biannual census data collection, which will be used to adaptively allocate treatment assignments after the first year. Communities will keep their group assignment for 4 distributions. Antimicrobial resistance will be monitored in a random subsample of treated and untreated children and adults in the Dosso region. See Figure 1 for a summary of the design.

Details are provided in the Protocol document, INV\_002454\_2019.

### **Mortality/Resistance Trial Interventions**

Communities will be randomized to the following 3 arms, with the allocation updated after a run-in period of 1 year according to the effect of each on the mortality rate among children aged 1-59 months as determined by inter-census intervals:

- Azithromycin 1-11: biannual weight- or height-based dose of oral azithromycin suspension to children 1-11 months old and oral placebo to children 12-59 months old
- Azithromycin 1-59: biannual weight- or height-based dose of oral azithromycin suspension to children 1-59 months old
- Placebo: biannual weight- or height-based dose of oral placebo to children 1-59 months old

### **3.2.2. Randomization**

AVENIR includes two cluster randomized trials (mortality/resistance and delivery), with grappes as the unit of randomization. Throughout we will refer to grappes as “communities”.

#### **Mortality/Resistance Trial**

At the start of the trial, communities will be allocated equally across the three arms, 1:1:1. After a run-in period of 1 year, the trial will update allocation probabilities every 6 months, corresponding to each census. Allocation probabilities between the arms will adapt based on the probability of that arm being the superior arm with respect to the mortality rate among children 1-59 months, so that newly enrolled communities will have a higher probability of being allocated to the arm with the lowest mortality rate. To minimize the impact of a possible carry-over effect of treatment in the event that a community changes arms through adaptive allocation, each community will stay with its randomized assignment for 4 distributions (approximately 2 years). Note that no community will be re-randomized by the time of the primary outcome.

#### **Response Adaptive Allocation Algorithm**

We will use the following algorithm for the adaptive allocation. Given all outcome measurements available at a given time, we will fit a negative binomial model to the data with

indicators for each arm (see section 6.2 for analysis details). From the model, we will estimate each arm's log mortality rate and its standard error. We will then draw 10,000 replicates of log mortality rates from the estimated distributions, assuming they are normally distributed, and in each draw of the joint distribution we will determine which arm has the lowest mortality rate. We will estimate the probability that each arm has the lowest mortality rate as the proportion of 10,000 replicates in which the arm has the lowest mortality rate. Following calculation of the probability that each arm has lowest mortality, we will then use a root transform of the probabilities to yield the allocation probabilities. Specifically, if  $p_i$  is the probability that arm  $i$  ( $i = 1,2,3$ ) yields the best outcomes, then compute the allocation probabilities  $a_i = p_i^\gamma / \sum_{j=1}^3 p_j^\gamma$ . We pre-specified a tempering value known only to the unmasked team to ensure masking:  $\gamma = 1/4$  or  $1/6$  or  $1/8$ . This transformation will help mitigate violent swings in allocation due to chance alone. Finally, we will not allow any arm's allocation probability to fall below 10% to preserve our ability to compare it against alternatives through the primary endpoint.

### 3.2.3. Sample size

We anticipate conducting the study in five regions of Niger: Dosso, Tahoua, Maradi, Zinder, Tillabéri; full details are given in the Protocol.

For the first two years, we expect approximately 1,400 communities in Dosso to participate for two full years (4 inter-census intervals of six month duration) and approximately 975 communities from Tahoua to participate for one year (2 inter-census intervals of six month duration) and 975 more communities from Tahoua to participate for half a year (1 inter-census interval). The sample size calculations below were informed by mortality rates and standard deviations measured in the MORDOR Niger trial [2].

Mortality rate measured as deaths per 1,000 person-years at risk will be the primary mortality outcome. The use of mortality rate protects against delays in start time across communities due to security or logistical issues, as person-time at risk naturally accounts for different follow-up times. Delayed implementation or exclusion of additional communities for security concerns could result in fewer inter-census intervals. *The sample size calculation assumes 8,525 inter-census intervals and 1,116 communities per arm.*

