4.3. Timeline

The study will take place over a 4-year period beginning Fall 2020 (Table 1).

Implementation will be phased in by region. Study progress is defined in “census rounds” which refer to a single 6-month census data collection and treatment period, and “inter-census intervals”, which refer to the interval between two census rounds, required to assess the primary outcome of mortality in the Mortality Trial. Dosso will be enrolled in the first year and Tahoua in the second year. Parts of Tahoua and Maradi will be added to the Programmatic Trial in the second and third years.

Table 1. Estimated eligible study population and communities with intervention roll out in Stage I and II.

Region	Stage I ¹							Stage II ²		
	Estimated eligible under-5 population ³	Estimated eligible communities	Year 1		Year 2		Year 3	Year 3		Year 4
			Round 1	Round 2 ⁴	Round 3 ⁵	Round 4	Round 5	Round 6	Round 7	Round 8
Dosso	271,273	1,800	X*	X	X	X*	X*	X	X	X
Tahoua (1)	245,944	1,225			X	X*	X	X	X	X
Tahoua (2)	245,944	1,225				X	X	X	X	X
Maradi (1)	342,889	1,000					X	X	X	X
Maradi (2)	342,890	2,000						X	X	X
Zinder	452,241	3,860							X	X
Tillabéri	440,791	3,070								X
Total:	2,341,972	14,180								

X = census and/or treatment; X* = census and/or treatment + resistance collections in a sample of communities

¹Stage I through primary outcome analysis at 2.5 years from the first enrollment.

²Stage II dependent upon primary outcome, resources, and security restrictions.

³As estimated from projections by the Institute for Health Metrics and Evaluation multiplied by fraction of eligible grappes in each region.

⁴Delivery trial will begin at the beginning of round 2 in year 1

⁵Interim analysis at approximately 1.5 years (end of round 3). At this time, intervention will begin in Programmatic Trial Communities.

Table 2. Estimated eligible population by trial and region for Stage I.

Region	Estimated eligible under-5 population ¹	Estimated eligible communities ²	Mortality/Resistance trial communities ^{3,4}	Delivery trial communities	Programmatic communities
Dosso	271,273	1,744	1,584	160	0
Tahoua	491,888	1,916	1,416	0	500
Maradi (1 st half)	342,889	1,000	0	0	1,000
Total	1,106,050	4,660	3,000	160	1,500

¹As estimated from projections by the Institute for Health Metrics and Evaluation multiplied by fraction of eligible grappes in each region.

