4.4.5. Sample size

4.4.5.1. Overview

We estimate that there are approximately 14,180 eligible communities encompassing approximately 2.3 million children under 5 across the 5 eligible regions (Table 1). For the first stage of the study, we estimate we will include 4,660 eligible communities in Dosso, Tahoua, and part of Maradi, with a total of 1.1 million eligible children under 5 (Table 2).

Stage I includes data collected through the primary outcomes. In Stage I, 3,000 communities will be selected for the Mortality/Resistance Trial, 160 for the delivery trials, and 1,500 will receive for the Programmatic Trial. The remaining eligible communities in Maradi, Zinder and Tillabéri will be included in the study during Stage II. Table 2 details the Stage I study population by region.

Refer to SAP for details of power calculations based on this sample size.

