#### ***Mortality primary outcomes***

*Mortality primary outcome 1:* mortality in 1-59 month olds, assessed at 2.5 years (based on at most 2 years of follow-up per community), comparing the 1-59 month and the placebo arms. Assuming a standard deviation of approximately 0.023, we find that 1,116 communities per arm will provide approximately 80% power to detect a 10% relative reduction, assuming a baseline mortality rate of 27 per thousand person-years among children 1-59 months old and an alpha of 0.05. The absolute effect size is a mortality rate difference of 2.7 deaths per 1000 person-years. This calculation is based on the standard Z-test formula for power (treating the mortality rate in each community as a continuous variable). The calculation does not involve a correction for multiple comparisons since the analysis uses a hierarchical testing approach for the three mortality outcomes, as described below.

*Mortality primary outcome 2:* mortality in 1-11 month olds, assessed at 2.5 years (based on at most 2 years of follow-up per community), comparing the 1-11 month arm and the placebo arm. Assuming a standard deviation of approximately 0.074, we find that 1,116 communities per arm will provide approximately 80% power to detect a 19% relative reduction, assuming a baseline

mortality rate of 45 deaths per thousand person-years among children 1-11 months old and an alpha of 0.05. The absolute effect size is a mortality rate difference of 8.8 per 1000 person-years. This calculation is based on the standard Z-test formula for power (treating the mortality rate in each community as a continuous variable). The calculation does not involve a correction for multiple comparisons since the analysis uses a hierarchical testing approach for the three mortality outcomes, as described below.

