*Mortality primary outcome 3:* mortality in 12-59 month olds, assessed at 2.5 years (based on at most 2 years of follow-up per community), comparing the 1-11 month and 1-59 treatment arms. Assuming a standard deviation of approximately 0.022, we find that 1,116 communities per arm will provide approximately 80% power to detect a 11% relative reduction, assuming a baseline mortality rate of 24 deaths per thousand person-years among children 12-59 months old and an alpha of 0.05. This corresponds to an absolute reduction of 2.7 in the death rate per 1000 person-years. This calculation is based on the standard Z-test formula for power (treating the mortality rate in each community as a continuous variable).

Sensitivity analyses for primary outcomes based on reduced enrollment caused by security or logistical concerns: if only the first half of Tahoua communities are enrolled by 2.5 years, with 791 communities per arm, we anticipate the following detectable relative detectable effect sizes (respectively): 12%, 23% and 13%, for 1-59 months, 1-11 months and 12-59 months.

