### 3.5.2. Analysis methods

#### Mortality in the mortality/resistance trial

Our parameter of interest for comparisons of mortality between arms is the relative reduction in mortality measured by the incidence rate ratio (IRR). The primary analysis will be a Poisson regression that includes the count of deaths as the outcome and the community-level person-time at risk as an offset, with observations for each community's inter-census interval. The model will include an indicator variable for each active treatment arm. The adaptive allocation will be accounted for using pooled regression, including in the model additional indicator variables for each of three allocations in the trial (the initial, equal allocation plus 2 adaptations). For community  $i$  and randomization  $j$  ( $j = 1, 2, 3$ ), the model will be:

$$\log(Y_{ij}) - \log(T_{ij}) = \alpha + \beta A_{ij} + \sum_{j=2}^3 \gamma_j P_j,$$

where  $Y_{ij}$  is the number of deaths and  $T_{ij}$  is the person-time at risk in that community;  $A_{ij}$  is a treatment indicator that will vary by each comparison (details below), and  $P_j$  is an indicator for the two adaptive random allocations (the first equal allocation is the omitted category). We will

estimate 95% confidence intervals for the IRRs using bootstrap resampling (10,000 replicates) that resamples communities with replacement and re-estimates the IRRs.

For primary outcome 1 that compares mortality among 1-59 month olds, we will include in the analysis children ages 1-59 months in the 1-59 month treatment arm and placebo arm.  $A_{ij}$  will be an indicator of allocation to the 1-59 month treatment arm, and  $\exp(\hat{\beta})$  will estimate the IRR.

For primary outcome 2 that compares mortality among children ages 1-11 months, we will subset the analysis to children ages 1-11 months enrolled in the 1-11 month treatment arm and placebo arm.  $A_{ij}$  will be an indicator of allocation to the 1-11 month treatment arm, and  $\exp(\hat{\beta})$  will estimate the IRR.

Similarly, for primary outcome 3 that compares mortality among children ages 12-59 months, we will subset the analysis to children ages 12-59 month in the 1-11 month treatment arm and 1-59 month treatment arm.  $A_{ij}$  will be an indicator of allocation to the 1-59 month treatment arm, and  $\exp(\hat{\beta})$  will estimate the IRR.

Secondary mortality analyses will be estimated similarly from the model subset to the appropriate age range.

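### The SAP's 80% power is for 3,350 communities in three equal arms; the protocol enrols 3,000, nearly half of them by adaptive allocation

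*SAP*

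**What the plan says.** SAP 3.2.3 expects about 1,400 Dosso communities with four inter-census intervals each, 975 Tahoua communities with two, and 975 more with one. It then states: "The sample size calculation assumes 8,525 inter-census intervals and 1,116 communities per arm". For mortality primary outcome 1 it reports: "we find that 1,116 communities per arm will provide approximately 80% power to detect a 10% relative reduction". Outcomes 2 and 3 use the same 1,116 per arm, with detectable reductions of 19% and 11%. The method is a two-sample Z-test that treats each community's rate as a continuous variable. The only sensitivity case is "if only the first half of Tahoua communities are enrolled by 2.5 years, with 791 communities per arm", with detectable reductions of 12%, 23% and 13%.

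Protocol 4.4.5.1 says: "In Stage I, 3,000 communities will be selected for the Mortality/Resistance Trial, 160 for the delivery trials". Table 2 in Protocol 4.3 ("Estimated eligible population by trial and region for Stage I") splits the 3,000 into 1,584 in Dosso and 1,416 in Tahoua. Section 4.4.5.1 then directs the reader: "Refer to SAP for details of power calculations based on this sample size".

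On allocation, Protocol 4.4.3.2 randomizes Dosso 1:1:1 and lets later regions adapt. SAP 3.2.2 allocates by a tempered probability that each arm has the lowest mortality, and does not let any arm's "allocation probability to fall below 10% to preserve our ability to compare it against alternatives". SAP 3.5.2 plans a "Poisson regression that includes the count of deaths as the outcome and the community-level person-time at risk as an offset".

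**The concern.** The two documents size the same trial differently, and the protocol's cross-reference leads to a calculation for another number of communities. The calculation also assumes three equal arms, although the 1,416 Tahoua communities are to be allocated unequally whenever the arms appear to differ.

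Outcomes 1 and 2 are both comparisons with placebo, the arm that shrinks if azithromycin works. Outcome 1 comes first in the fixed-sequence procedure of SAP 3.3.1, so its power limits the chance that outcomes 2 and 3 are tested formally at all. A reader who has to interpret a non-significant outcome 1 needs the detectable effect for the trial as run.

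**Working it through.** **Inputs.** From SAP 3.2.3, per 1,000 person-years: SDs 23, 74 and 22; baseline rates 27, 45 and 24; absolute effects 2.7, 8.8 and 2.7; alpha 0.05, two-sided (SAP 3.2.4). From Protocol Table 2: 1,584 and 1,416 communities.

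**Formulas.** Power = Φ(Δ / (SD·√(1/n₁ + 1/n₂)) − 1.96). Detectable effect at 80% power = (1.96 + 0.8416)·SD·√(1/n₁ + 1/n₂).

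**1. Counts.**
- SAP: 1,400 + 975 + 975 = 3,350, and 3,350/3 = 1,116.7 per arm. Intervals: 1,400×4 + 975×2 + 975×1 = 8,525. Both SAP figures reproduce.
- Protocol: 1,584 + 1,416 = 3,000, or 1,000 per arm if equal.

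**2. The SAP's power, then the protocol's size (equal arms).** For outcome 1 at 1,116 per arm, the standard error is 23·√(2/1,116) = 0.974, and 2.7/0.974 − 1.96 = 0.81, giving 79.2%. At 1,000 per arm the standard error is 1.029, and 2.7/1.029 − 1.96 = 0.665, giving 74.7%.

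| Outcome | Power, 1,116 | Power, 1,000 | Detectable, 1,116 | Detectable, 1,000 |
|---|---|---|---|---|
| 1 (2.7) | 79.2% | 74.7% | 2.73 (10.1%) | 2.88 (10.7%) |
| 2 (8.8) | 80.2% | 75.8% | 8.78 (19.5%) | 9.27 (20.6%) |
| 3 (2.7) | 82.6% | 78.4% | 2.61 (10.9%) | 2.76 (11.5%) |

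With the SAP's percentages in place of its absolute effects, outcome 2 (19% of 45 = 8.55) goes from 77.9% to 73.4%, and outcome 3 (11% of 24 = 2.64) from 80.9% to 76.5%.

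**3. Which unit the SAP counts.** At 791 per arm with fixed SDs, the detectable effects are 12.0%, 23.2% and 12.9%, matching the SAP's 12%, 23% and 13%. Scaling that case by intervals instead (1,400×4 + 975×2 = 7,550; 1,116×7,550/8,525 = 988 per arm) gives 10.7%, 20.7% and 11.6%, which do not match. The SAP counts communities.

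**4. The alternative unit.** Assume Tahoua enters in two equal halves of 708. Intervals are then 1,584×4 + 708×2 + 708×1 = 8,460. Effective n is 1,116×8,460/8,525 = 1,107.5 per arm, and equal-arm power is 78.9%, 79.9% and 82.3%.

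**5. Unequal allocation.** Dosso gives 528 per arm.

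*Floor.* If placebo gets 10% of Tahoua throughout, it has 528 + 141.6 ≈ 670 communities. Power then depends on how the other 90% is split:

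| Azithro 1–59 share of Tahoua | Outcome 1 | Outcome 2 (8.8) | Outcome 3 (2.7) |
|---|---|---|---|
| 45% | 67.8% | 68.9% | 84.2% |
| 60% | 70.3% | 65.5% | 83.0% |
| 80% | 72.7% | 58.5% | 76.5% |

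*Simulation of the SAP algorithm.* There were 4,000 trials for each tempering value (1/4, 1/6, 1/8), with 10,000 draws per allocation. Assumed true rates at 1–59 months are 24.3 (azithro 1–59), 25.7 (azithro 1–11) and 27.0 (placebo). The first look uses two Dosso intervals. The second adds a third Dosso interval and the first Tahoua interval. Interim variance was handled in two ways: (a) SD 23 taken as the four-interval value and scaled to follow-up; (b) SD 23 taken as already reached at one year.

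- Mean placebo arm for 1/4, 1/6, 1/8: (a) 831, 877, 902; (b) 771, 823, 855.
- Placebo at the floor at both looks: (a) 5.3%, 1.1%, 0.9% of trials; (b) 14.9%, 3.9%, 3.6%.
- Power counting communities: 72–74% (outcome 1), 69–73% (outcome 2), 80–81% (outcome 3).
- Power counting intervals: about 78–79%, 77–79% and 83–84%.

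**6. Reduced enrolment.** The SAP's 791 is (1,400 + 975)/3 = 791.7, rounded down. The protocol equivalent is (1,584 + 708)/3 = 764, with detectable effects of 12.2%, 23.6% and 13.1%.

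**The case against.** The strongest reply is that holding the SD per community fixed is the least favourable reading. Under the protocol's counts, communities with four intervals rise from 42% (1,400/3,350) to 53% (1,584/3,000), so the average community rate is less noisy. If variance is inversely proportional to the number of intervals, the SAP's unweighted Z-test gives 79.1%, 80.1% and 82.5% at 1,000 per arm. If only half the variance scales that way, it gives 76.9%, 77.9% and 80.4%. The planned Poisson model with a person-time offset also gives weight to follow-up. This stands: the equal-arm loss lies between almost nothing and about 4.5 points, and the documents do not say where. But the SAP's published calculation uses the fixed SD, as its 791 case shows, so the restatement is needed on either view.

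The data cut matters too. SAP 3.2.6 places the primary analysis two years after enrolment is complete, whereas 3.2.7 uses 2.5 years from first enrolment. Under the later cut, with four intervals for every community (3,000×4 = 12,000; effective n 1,116×12,000/8,525 = 1,571), interval scaling gives about 91–93%. The power section itself assumes the 2.5-year cut, so that is the basis used here.

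The 791 case does bracket 1,000 per arm, but it is a contingency with equal arms, built on the same superseded counts. The 10% floor and the tempering show that the authors saw the allocation risk, yet the printed power text does not quantify it. The companion power notebook was not available and may contain more. Finally, the simulation rests on one assumed set of rates; the documents give none for azithro 1–11 at 1–59 months.

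**Conclusion.** The concern holds. The SAP's arithmetic is internally correct, but it describes 3,350 communities in equal arms and not the 3,000 that the protocol enrols. On the SAP's own formula, equal arms of 1,000 give 74.7%, 75.8% and 78.4%. Adaptive allocation moves outcomes 1 and 2 to about 72–74% and 69–73% and leaves outcome 3 near 80%, under the assumed rates. If information follows inter-census intervals, the loss is small for all three. The floor case (about 68–73% for outcome 1 and 59–69% for outcome 2) is an unlikely worst case.

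This does not threaten the validity of the trial. It should be corrected because the protocol relies on the SAP for this figure and because outcome 1 gates the rest of the sequence.

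**What to change.** In SAP 3.2.3, reconcile 3,350 with 3,000 and replace the 80% statements with power and detectable effects for 1,584 Dosso communities (1:1:1) plus 1,416 Tahoua communities (adaptive). Show equal, expected and floor allocation for each of the three tempering values, and label the floor as an unlikely worst case. Preferably simulate the allocation algorithm together with the planned Poisson and permutation analysis, so that both communities and follow-up count. State the assumed rates, with a range, and the data cut. Keep the reduced-enrolment case but rebuild it on the protocol's counts (764 per arm if half of Tahoua is enrolled).

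The cost is SAP wording and a rerun of the existing power notebook, extended if the simulation is added. At the 2.5-year cut the stated power is likely to look slightly less favourable. No added enrolment is needed, and the estimand, model, alpha and test order do not change.
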